14.6. Documenting Adverse Events

All AEs, including SAEs, are to be accurately recorded on the Adverse Event page of the subject's eCRF from the time the subject signs the informed consent through 90 days after the subject's last dose of any study drug. Each event will be assessed for serious criteria, severity, and causality ([Section 14.5](#)). The date of onset, as well as the duration of the event will be recorded. In addition, treatments provided to the subject, actions taken with the study drugs, and the outcome of the AE will also be noted.

14.7. Reporting Serious Adverse Events (SAE), and Adverse Events of Special interest (AESI)

14.7.1. Time Frame for Reporting

All SAEs and AESIs must be reported to the sponsor or sponsor designee within 24 hours of awareness, regardless of initiation of new anticancer therapy including the following:

- Any SAE or AESI experienced by the subject from the signing of informed consent to 90 days after the last dose of any study drug, regardless of relationship to study drug.
- Any SAE or AESI that the investigator becomes aware of, and believes to be study drug-related, that occurs more than 90 days after the subject last received study drug.

All SAEs must be reported to the following fax line within 24 hours of awareness:

[REDACTED]
[REDACTED]
[REDACTED]

Additional data concerning the SAE (e.g., diagnostic test reports, hospital summaries, etc.) must be promptly reported (within 24 hours of receipt) to the sponsor or sponsor's designee, until resolution of the SAE. Should the FDA or National Regulatory Authorities require that the sponsor submit additional data on the event, the investigator will be asked to provide those data to the sponsor in a timely fashion.

14.7.2. Information to be Provided by the Investigator

Within 24 hours of becoming aware of the SAE or subject death, the investigator must notify the sponsor or designee and transmit information to the sponsor or designee. Information (initial and follow-up) should be provided on an electronic and/or paper SAE Report form signed and dated by the investigator. The SAE Report form and copies of source documents with subject identifiers redacted will be transmitted by fax. A hospital discharge summary should be provided if the subject was hospitalized. An SAE report will be considered final once all relevant information has been received and reviewed by the sponsor.

The SAE report form is provided in the investigator study files. Please refer to the investigator study files for instructions on how to complete these forms. The investigator will provide all the following information related to the event:

- Investigator identification
- Subject identification (e.g., subject number, initials, sex, age or date of birth)
- Information regarding study drug administration (e.g. start/stop date, dose, and frequency)
- Day of SAE occurrence documentation on SAE form
- Description of event
- Action taken with the study drugs in relation to the SAE
- Outcome of the SAE

In addition to the above information, the investigator must provide, for each event term, an assessment of:

- Severity/intensity
- Relationship to the study drug (causality assessment)

14.8. Sponsor and Investigator Responsibility for Reporting Adverse Events

All AEs and SAEs will be reported to regulatory authorities, IRBs/IECs, and investigators in accordance with all applicable global laws and regulations, including but not limited to 21 CFR 312.32. The investigator must submit all Safety Letters received from the sponsor to his/her

IRB/IEC per agreements and local requirements. The investigator must keep copies of all safety reports/letters, including correspondence with Ziopharm and the IRB/IEC, in the study file.

14.9. Follow-up Information for Adverse Events

Appropriate diagnostic tests should be performed and therapeutic measures, as medically indicated, should be instituted. Appropriate consultation and follow-up evaluations should be carried out until the event has resolved, stabilized, returned to baseline, or is otherwise explained by the investigator.

14.9.1. Required Follow-up for Adverse Events

All treatment-emergent AEs and SAEs will be collected through 90 days after the last dose of any study drug). All the AEs and SAEs should be followed up by the next study visit of the AE/SAE be aware of; all the related AEs and SAEs should be followed up until:

- The event resolves
- The event returns to baseline, if a baseline value is available
- The event stabilizes (following consultation and agreement by the Ziopharm Medical Monitor)
- The event can be attributed to factors other than the study drug or other than study procedure

14.10. Pregnancies

Subjects who become pregnant during the study should immediately discontinue participation in the study. The sponsor should be immediately notified.

[figure not shown]
An initial Pregnancy Report form, and a Pregnancy Outcome Form are to be completed by the investigator or designee. The Pregnancy Report form, and the completion guidelines will be provided in the investigator study files. Please refer to the investigator study files for details on how to complete these forms.

14.11. Overdose

Investigational product overdose of study subject, with or without associated AEs/SAEs, should be reported within 24 hours of awareness to sponsor ([REDACTED]

[REDACTED] All AEs or SAEs as a result of overdose should be reported as described previously in [Section 14.6](#) and [Section 14.7](#).

15.

[REDACTED]
[REDACTED]
[REDACTED].

16. STATISTICAL METHODS

This is an uncontrolled single arm study to determine whether the intratumoral Adenovirus [REDACTED] (Ad-RTS-hIL-12) and oral (PO) veledimex (RTS activator ligand) in combination with cemiplimab-rwlc (Libtayo®) is effective based on the estimate of Overall Survival (OS) when treating subjects with recurrent or progressive glioblastoma. Where applicable, estimates of OS and other surrogate endpoints will be compared with well-matched historical control data to determine whether the estimates obtained in this study will be viewed as promising to support further development of this experimental combination of treatments. All populations for analyses and the types of analyses to be performed will be defined in more detail in the statistical analysis plan (SAP).

16.1. Populations for Analysis

- The safety population will comprise all subjects who have received at least one dose of any of the investigational agents: cemiplimab-rwlc, the injection of Ad-RTS-hIL-12 or any doses of veledimex
- The per protocol population will comprise subjects who have received Day -7 of cemiplimab-rwlc, the injection of Ad-RTS-hIL-12 with at least one post Ad-RTS-hIL-12 dose of veledimex, at least one post Ad-RTS-hIL-12 dose of cemiplimab-rwlc (e.g., Day 15), and who have not had a major protocol violation (i.e., subjects who have had minor protocol violation(s) that are deemed not to impact efficacy will be included in this analysis population.)
- [REDACTED]

16.2. Sample Size and Power Calculations

We plan to accrue up to 36 subjects to obtain approximately 25 subjects evaluable for efficacy. This patient population will be heterogeneous and as such, it is difficult to define a clear safety threshold for evaluation in combination with determination of OS, ORR and PFS.

[REDACTED]

A sample size of up to 25, will allow us to estimate an overall safety rate with a maximum 95% exact confidence interval half-width of approximately 0.19 [REDACTED]

[REDACTED] In addition, a Toxicity boundary based on repeated significance testing provides for a guideline to seriously consider stopping the trial if the number of subjects experiencing unacceptable toxicity exceeds the proportions below assuming a 30% Toxicity rate is acceptable and 60% would be unacceptable:

Low boundary: 3/5 5/10 8/15 9/20 11/25

High boundary: 3/5 6/10 8/15 10/20 11/25

According to boundary conditions stated herein, a review will be performed after 5, 10, 15, 20 and 25 subjects reach Day 30. Serious consideration for stopping the clinical trial should be given if the number of subjects meeting the Stopping Rules criteria is determined to be greater than 3/5, 5/10, 8/15, 9/20, or 11/25, the values which form the lower boundary condition. For

clinical study purposes, the lower bound will always be crossed first triggering the decision rule. The Stopping Rules are defined in section 10.9. The toxicity boundaries assume an alpha=0.1 and beta=0.1 for a power of 90%.

The method for determination of the Toxicity boundary used the Toxbdry function in the Clinfun R package implementation of repeated significance testing methodology (Ivanova et al. 2005, Jennison and Turnbull 2000). The operating characteristics of the boundary conditions will be specified in a separate statistical analysis plan (SAP).

If the study continues to completion, a sample size of 25 to 30 subjects provides for an estimate of OS at a point in time with (at most) approximately 10% standard error of the estimate assuming the binomial estimation method.

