4. STATISTICAL METHODS

4.1. Sample Size

Sample Size and Power Calculations

Based on Amendment 2, the plan was updated to accrue up to 36 subjects instead of 30 subjects (originally planned) to obtain approximately 25 subjects evaluable for efficacy.

A sample size of up to 25, will allow us to estimate an overall safety rate with a maximum 95% exact confidence interval half-width of approximately 0.19.

In addition, a Toxicity boundary based on repeated significance testing provided for a guideline to seriously consider stopping the trial if the number of subjects experiencing unacceptable toxicity exceeded the proportions below. The method for determination of the Toxicity boundary used the Toxbdry function in the Clinfun R package implementation of repeated significance testing methodology ([Ivanova, Qaqish, & Schell, 2005](#)).

Low boundary: 3/5, 5/10, 8/15, 9/20, 11/25

High boundary: 3/5, 6/10, 8/15, 10/20, 11/25

The boundaries above were created assuming a 30% Toxicity rate is acceptable and 60% would be unacceptable. According to boundary conditions stated herein, a review was to be performed if applicable, after 5, 10, 15, 20 and 25 subjects reach Day 30. Serious consideration for stopping the clinical trial should be given if the number of subjects meeting the Stopping Rules criteria is determined to be greater than 3/5, 5/10, 8/15, 9/20, or 11/25, the values which form the lower boundary condition. The operating characteristics of the boundary conditions are calculated and displayed below.

Operating Characteristics:

Prob toxicity	Prob Cross. lower	Prob Stop lower	Expected Sample Size lo	Prob Cross. Hi bound	Prob Stop hi	Expected Sample Size hi
0.30	0.101	0.090	23.8	0.074	0.050	24.2
0.36	0.239	0.205	22.3	0.193	0.122	23.2
0.42	0.441	0.377	20.2	0.388	0.248	21.6
0.48	0.661	0.578	17.5	0.617	0.426	19.3
0.54	0.839	0.763	14.6	0.812	0.625	16.5
0.60	0.943	0.894	11.9	0.932	0.800	13.6

This patient population will be heterogeneous and as such, it is difficult to define a clear safety threshold for evaluation in combination with determination of OS, ORR and PFS.

Assuming the binomial estimation method, if the study continues to completion, a sample size of 25 to 30 subjects provides for an estimate of OS at a point in time with approximately 10% standard error of the estimate.

Enrollment objectives:

- [REDACTED]

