4.7.1. Overview of Statistical Summaries by Defined Populations

Subject populations will be evaluated and used for presentation and analysis of the following:

- The FAS will be used for summaries of subject disposition, baseline characteristics and for safety. In addition, the FAS will be used in secondary analyses of OS, ORR, and PFS.
- The PP population is to be used for the primary analysis of OS, ORR, PFS and OS.
- When applicable the ESP will be used for analysis of dose limiting toxicities.
- [REDACTED]

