9. SAFETY ANALYSIS

All analyses of safety will be conducted using the FAS. Abnormal laboratory test results, will be captured as Adverse Events (AE)s. Safety evaluations will use calculations to determine estimates of the incidence, intensity, and the type of AE and SAE's based on preferred term coding.

All clinical findings will be further inspected through a clinical review of relevant parameters including AEs, serious adverse events (SAEs), laboratory values (hematology, serum chemistry, and urinalysis), body weight, vital signs, physical examinations, and ECOG performance status. Where applicable the Safety will also be summarized using the ESP. Exposure to study drug and reasons for discontinuation of study treatment will be tabulated.

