9.1.3. Incidence of Adverse Events

An overview summary of the number and percentage of subjects with any TEAE, serious TEAE, study drug-related TEAE, study drug-related serious TEAE, TEAE leading to treatment discontinuation, TEAE leading to study termination, and AE leading to death will be presented.

Summaries of the total number of TEAEs and the number and percentage of subjects with at least one TEAE will be provided. The number and percentage of subjects and the number of events will also be presented by SOC and PT. At each level of summarization, a subject is counted once if the subject reported one or more events. Percentages will be calculated out of the number of subjects in the FAS. The number of events at each level of SOC and PT will also be summarized.

A summary of TEAEs will also be presented in descending order from the SOC with the highest total incidence to the SOC with the lowest total incidence. If the total incidence for any two or more SOCs is equal, the SOCs will be presented in alphabetical order. Within each SOC, the PTs will be presented in alphabetical order.

All AEs will be provided in subject listings.

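### The overall safety rate used to justify the sample size is never defined or estimated in the SAP, and its stated precision of 0.19 is 0.204 at n = 25

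*Protocol*

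**What the plan says.** Protocol 16.2 gives two safety arguments for the sample size. The first is precision: a sample of up to 25 "will allow us to estimate an overall safety rate with a maximum 95% exact confidence interval half-width of approximately 0.19". The second is a toxicity boundary with looks at 5, 10, 15, 20 and 25 subjects, "assuming a 30% Toxicity rate is acceptable and 60% would be unacceptable". The event counted by the boundary is a subject meeting the Stopping Rules criteria of Section 10.9. SAP 4.1 carries both arguments forward ("The boundaries above were created assuming a 30% Toxicity rate is acceptable and 60% would be unacceptable") and tabulates the boundary's operating characteristics.

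The primary safety endpoint in the protocol synopsis is the safety profile. For its analysis, SAP Section 9 states: "Safety evaluations will use calculations to determine estimates of the incidence, intensity, and the type of AE and SAE's based on preferred term coding". SAP 9.1.3 plans "An overview summary of the number and percentage of subjects with any TEAE, serious TEAE, study drug-related TEAE", followed by related serious events, discontinuations and deaths. Later subsections cover relationship, severity, SAEs, deaths and laboratory data.

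On toxicity as such, SAP 4.7.1 says only this: "When applicable the ESP will be used for analysis of dose limiting toxicities". The output lists in the SAP appendices include Table 14.3.13, Dose Limiting Toxicities, for the Per Protocol population.

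**The concern.** The documents name a per-subject safety rate, state how precisely it will be estimated, and monitor a closely related per-subject event. The analysis plan then contains no such rate. The adverse event tables cannot supply it afterwards. Rows by preferred term overlap within subjects and cannot be added up, and none of the 9.1.3 overview categories is the Section 10.9 event.

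Safety is half of the primary objective. A report that follows the SAP would describe the events well. It would not give the proportion of subjects with the toxicity that was monitored, or how uncertain that proportion is. A reader could not see where the result lies relative to the two rates on which the monitoring was designed.

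**Working it through.** **1. The stated precision.** Inputs: n = 25 and an exact two-sided 95% interval (Protocol 16.2, SAP 4.1). For x events in n subjects the Clopper-Pearson limits are L = Beta quantile(0.025; x, n − x + 1) and U = Beta quantile(0.975; x + 1, n − x). The half-width is (U − L)/2, maximised over x.

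| n | Source of n | x at maximum | L to U | Maximum half-width |
|---|---|---|---|---|
| 25 | Protocol 16.2 | 12 (or 13) | 0.278 to 0.687 | 0.204 |
| 28 | for comparison | 14 | | 0.194 |
| 30 | upper end of the 25 to 30 range in 16.2 | 15 | 0.313 to 0.687 | 0.187 |
| 36 | planned accrual | 18 | | 0.171 |
| 40 | FAS, SAP 4.4 | 20 | 0.338 to 0.662 | 0.162 |

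The stated 0.19 is not reproduced at 25. The normal approximation gives 1.96 × √(0.25/25) = 0.196 and the Wilson interval gives 0.182, but neither is exact. The exact value reaches about 0.19 at 28 to 30 subjects. Section 16.2 of the original protocol version, in the same file, attaches 0.19 to a sample of up to 30, where 0.187 fits. That is a possible source of the figure, not a proven one.

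**2. The boundary.** An exact binomial recursion over the five looks, crossing when the count is strictly greater than 3, 5, 8, 9 and 11, gives a crossing probability of 0.101 at a true rate of 30% and 0.943 at 60%. Expected sample sizes are 23.8 and 11.9. These match the SAP table, so the monitoring rule is correctly described. Its last look is at 25 subjects; 40 − 25 = 15 treated subjects lie beyond it.

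**3. Is the rate estimated anywhere?** Confidence intervals are specified for OS, PFS, pseudo-progression and ORR (SAP 8.2 and 8.3). None is specified in Section 9. Redaction does not explain this: the SAP contents list runs from 9.1 to 9.5 without a gap. The visible text of SAP Section 10 does not list the rate among the dropped analyses.

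**4. The nearest output.** For dose limiting toxicities, SAP 4.7.1 names the ESP and Table 14.3.13 names the Per Protocol population. The choice matters: Per Protocol requires a cemiplimab dose after the injection (SAP 4.5.3), so a subject whose toxicity prevented that dose would drop out of the table.

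**5. What the interval would show (illustrative counts, not data).** At n = 25, 11 events (44%) give 24.4% to 65.1%, which contains both 30% and 60%. At n = 40:

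| Events | Rate | Exact 95% CI |
|---|---|---|
| 12 | 30.0% | 16.6% to 46.5% |
| 17 | 42.5% | 27.0% to 59.1% |
| 18 | 45.0% | 29.3% to 61.5% |
| 19 | 47.5% | 31.5% to 63.9% |

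With 17 or fewer events the interval lies below 60%; with 19 or more it lies above 30%. Only 18 leaves both rates inside.

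**6. Event windows.** Section 10.9 uses Day -7 to Day 28 for related SAEs. For deaths not due to progression it runs to 30 days after the end of veledimex dosing, which on schedule is Day 14 + 30 = Day 44. The boundary reviews in 16.2 are at Day 30. The TEAE window in SAP 9.1.1 runs to 90 days after study drug stops.

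**The case against.** The strongest reply is that the primary safety endpoint is the safety profile, not a rate, and that the SAP does describe it: incidence, severity, relationship, SAEs, discontinuations, deaths and laboratory data. That stands. A reader might infer that the primary safety question goes unanswered. The documents do not support that reading.

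Second, a reader might infer that the SAP owes a final comparison with 30% and 60%. Those rates belong to a stopping guideline for interim looks, and its operating characteristics are in SAP 4.1 as the protocol promised. Both documents say that a clear safety threshold is hard to define, and SAP Section 8 plans no formal testing of primary or secondary endpoints. No unmet commitment to a test exists.

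Third, the precision sentence and the boundary are separate statements. Neither document says that the overall safety rate is the Section 10.9 event, and a worst-case half-width applies to any binomial proportion at that n. This is also correct. It means that the rate is undefined, so equating the two is a proposal and not something already in the plan.

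Fourth, the table shells are in a spreadsheet outside these documents, so the content of Tables 14.3.1.1 and 14.3.13 cannot be fully settled. The SAP text that should govern them still gives no definition and no interval.

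**Conclusion.** The point holds in a limited form. The plan justifies its size by estimating an overall safety rate with an exact interval, then neither defines nor estimates such a rate, and no safety proportion has an interval. The stated half-width is wrong at the stated n: 0.204, not 0.19, a shortfall of about 0.014. For the 40 treated subjects the maximum is 0.162, so the rate can be reported more precisely than promised.

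This is a gap in reporting. The adverse event analysis and the monitoring boundary are not invalidated, and no acceptance test is missing. The conclusion assumes that the unseen table shells do not already contain the rate, and that Section 10.9 status can be derived from the collected AE and SAE data. No dedicated eCRF field for it is visible.

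**What to change.** - In SAP 9.1.3, define the overall safety rate as the proportion of FAS subjects meeting the event the toxicity boundary already counts (the Section 10.9 criteria). Report n, percentage and a two-sided 95% Clopper-Pearson interval.
- Show it descriptively beside the 30% and 60% design rates, with no formal test. Keep it on a line separate from the TEAE rows, because their 90-day window differs.
- Have the sponsor reconcile the windows in Sections 10.9 and 16.2 before the variable is derived. State how the window ends for FAS subjects who received neither the injection nor veledimex.
- Have the sponsor define dose limiting toxicities for this trial and settle whether the ESP or the Per Protocol population applies.
- Correct the precision statement: maximum exact half-width 0.204 at n = 25 and 0.162 at n = 40.

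The cost is a short SAP edit, one extra variable derived from AE and SAE data, and one table line. The only downside is a slightly less favourable half-width at n = 25.

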Sample Size Determination	
We plan to accrue up to 36 subjects to obtain approximately 25 subjects evaluable for efficacy. This subject population will be heterogeneous and as such, it is difficult to define a clear safety threshold for evaluation in combination with determination of OS, ORR and PFS at 12 weeks. A sample size of approximately 25, will allow us to estimate an overall safety rate with a maximum 95% exact confidence interval half-width of approximately 0.19. Note: a minimum of 20 subjects undergoing subtotal resection will be required to ensure that enough subjects have measurable disease for evaluation of overall response rate per iRANO criteria.
 
In addition, a toxicity boundary based on repeated significance testing provides a guideline for stopping the trial if the number of subjects experiencing unacceptable toxicity exceeds the proportions below, assuming a 30% toxicity rate is acceptable and 60% would be unacceptable:
 
Low boundary: 3/5 5/10 8/15 9/20 11/25
 
High boundary: 3/5 6/10 8/15 10/20 11/25
 
Note: A sample size of 25 to 30 subjects provides for an estimate of OS at a point in time with (at most) a 10% standard error of the estimate assuming the binomial estimation method.

Study Duration	
The duration of this study from the time of initiating subject screening until the completion of survival follow-up is anticipated to be approximately 36 months, including 12 months for enrollment and 24 months of follow-up.
 
The start of study is defined as the date when the first subject is consented into the study and the study stop date is the date of the last subject's last visit.

Table 1: Schedule of Study Procedures

Activity	Screening	Treatment							
	Day -30 to -8*	Day -7 **	Day 0 ^a	Day 1	Day 2	Day 3	Day 4 to 6	Day 7	Day 8 to 13
Informed consent	X								
Medical/Cancer history ^d	X								
Physical exam ^e , including targeted neurological exam	X	X	X	X	X	X		X	
Karnofsky PS ^f	X	X	X						
Height (screen) and weight	X							X	
Vital signs ^g	X	X	X	X	X	X		X	
Adverse events ^h									CONTINUOUS
Concomitant medications ^h									CONTINUOUS
Survival status ⁱ									CONTINUOUS
Pregnancy test ^j	X	X	X						
Hematology ^k	X	X	X ^a	X	X	X		X	
Coagulation ^l	X		X ^a	X		X		X	
Serum chemistry ^m	X	X	X ^a	X	X	X		X	
Urinalysis ⁿ	X	X	X ^a			X		X	
Thyroid panel ^o	X								
ECG ^p	X		X			X		X	
Confirm eligibility		X ^q							
Cemiplimab-rwlc dose ^q		X							
Ad-RTS-hIL-12			X ^{r,s}						

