16.6.2. Safety Analyses

The safety population will be used to perform safety evaluations for all safety variables.

Safety evaluations will be based on the incidence, intensity, and type of AEs and SAEs. Clinically significant changes in the subjects' physical examinations, vital signs, and ECG evaluations, and abnormal laboratory values will be captured as AEs. Safety will also be assessed based on medical history and prior/concomitant medications.

The safety evaluation period extends from the date the patient signs the ICF until 90 days after the last dose of study drug, unless the patient discontinues the trial due to one of the following reasons:

- Documented progression
- Symptomatic deterioration also denoted as symptomatic progression
- AEs that the investigator feels will subsequently make the subject noncompliant with the protocol planned Schedule of Study Procedures
- Loss to follow-up
- Noncompliance with the protocol
- Other reason not listed above

All treatment-emergent AEs will be coded using the Medical Dictionary for Regulatory Activities (MedDRA) and will be tabulated by number and percent of subjects, and according to relationship to the study drugs, severity, and seriousness. Treatment-emergent is defined as any AE that occurs during or after administration of the first dose of study drug through the evaluation period for safety defined above, regardless of relationship to study drug; or any event that is present at baseline that worsens in intensity or is subsequently considered to be drug related by the investigator. Deaths, SAEs, and AEs resulting in study discontinuation will be listed.

Subjects who discontinue the trial as defined above will be followed for safety up to 90 days after discontinuation and until all safety events that have started during the safety evaluation period are classified as resolved or the end of the study is reached. After the conclusion of the safety evaluation period is triggered by a discontinuation event, the subject continues to be followed only for OS.

Listings of vital signs and physical examination data will be presented by visit.

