16.2. Sample Size and Power Calculations

We plan to accrue up to 30 subjects to obtain approximately 25 subjects evaluable for efficacy. This patient population will be heterogeneous and as such, it is difficult to define a clear safety threshold for evaluation in combination with determination of OS, ORR and PFS.

NOTE: a minimum of 20 subjects undergoing subtotal resection will be required to ensure that sufficient subjects have measurable disease for evaluation of overall response rate per iRANO criteria.

A sample size of up to 30, will allow us to estimate an overall safety rate with a maximum 95% exact confidence interval half-width of approximately 0.19. In addition, a Toxicity boundary based on repeated significance testing provides for a guideline to seriously consider stopping the trial if the number of subjects experiencing a grade 3 or grade 4 toxicity exceeds the proportions below assuming a 30% Toxicity rate is acceptable and 60% would be unacceptable:

Low boundary: 3/5 5/10 8/15 9/20 11/25

High boundary: 3/5 6/10 8/15 10/20 11/25

The method for determination of the Toxicity boundary used the Toxbdry function in the Clinfun R package implementation of repeated significance testing methodology ([Ivanova et al. 2005](#), [Jennison and Turnbull 2000](#)). The operating characteristics of the boundary conditions will be specified in a separate statistical analysis plan (SAP).

If the study continues to completion, a sample size of 25 to 30 subjects provides for an estimate of OS at a point in time with (at most) approximately 10% standard error of the estimate assuming the binomial estimation method.

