4.4. Data Management

Ziopharm Data Management directs and oversees the administration of the ATI001-204 eCRF database. The clinical trial data from all screened and enrolled subjects populate the ATI001-204 database which is also managed by a third-party contract research organization (CRO). In addition, the ATI001-204 protocol provided for study objectives for which the data obtained are not part of the eCRF. Instead, the data are acquired based on the data transfer agreements (DTA) from 7 external data sources denoted as “vendors” summarized in [Table 1](#) below. Specifically:

- The ATI001-204 clinical database consists of N=40 FAS subjects for whom at least one of the following study treatments were received: Ad-RTS-hIL-12, veledimex, cemiplimab.
- The imaging data objective originally to be undertaken with Bioclinica was put on hold and not performed.

- For completeness it is noted that there are subjects who also have data in the database who are classified as screen failures for whom we are not counting for the purpose of this description. Subjects that were enrolled but did not receive treatment were withdrawn and will not be included in any analysis population.
- A summary of the number of screen failures signing an informed consent is provided in the subject disposition.
- Extraction of Raw SAS datasets from the EDC database will be converted into Study Data Tabulation Model (SDTM) SAS datasets based on CDISC.

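### The maximum exact 95% confidence interval half-width for the safety rate at 25 subjects is about 0.20 (Clopper-Pearson), not the stated 0.19

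*Protocol*

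**What the plan says.** Three current places carry the statement. Protocol Section 16.2 says that up to 25 subjects will make it possible to "estimate an overall safety rate with a maximum 95% exact confidence interval half-width of approximately 0.19". The synopsis, under Sample Size Determination, has "A sample size of approximately 25, will allow us to estimate an overall safety rate" and attaches the same 0.19. SAP Section 4.1 gives up to 25 subjects "with a maximum 95% exact confidence interval half-width of approximately 0.19". None of them says which exact method was used.

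The 25 is the number expected to be evaluable for efficacy out of up to 36 accrued. Safety itself is analysed on a wider set. Protocol Section 16.6.2 says "The safety population will be used to perform safety evaluations for all safety variables", and that population is everyone who received any study agent. SAP Section 9 says "All analyses of safety will be conducted using the FAS". The SAP also gives the realised count in Section 4.4: "The ATI001-204 clinical database consists of N=40 FAS subjects".

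**The concern.** A maximum half-width is a worst case over all possible event counts, so it is fixed once n, the confidence level and the method are fixed. It can be checked directly, and 0.19 looked small for an exact interval on 25 subjects: the simple normal approximation at a rate of one half already gives 0.196.

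Safety is part of the primary objective, and this is the only precision quoted for the safety rate. If the figure is wrong, a reader is told that 25 subjects deliver slightly more precision than they do. Twenty-five is also the last look of the toxicity boundary (11/25), although that boundary does not use this interval.

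**Working it through.** **Inputs.** n = 25 (Protocol 16.2, synopsis, SAP 4.1); 95% two-sided; exact; maximum over all outcomes; stated result about 0.19.

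**Formula.** Clopper-Pearson limits for x events in n:

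- L = 0.025 quantile of Beta(x, n − x + 1), with L = 0 at x = 0
- U = 0.975 quantile of Beta(x + 1, n − x), with U = 1 at x = n
- half-width = (U − L)/2, maximised over x = 0, …, n

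**The plan's own figure.** At n = 25 the maximum is at x = 13 (x = 12 is its mirror image, 0.278 to 0.687):

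- 13/25: L = 0.3131, U = 0.7220
- half-width = (0.7220 − 0.3131)/2 = 0.2045

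The stated 0.19 is not reproduced. The gap is 0.2045 − 0.19 = 0.0145, and 0.0145/0.2045 = 7.1%. This is not one isolated count: the half-width exceeds 0.195 for every x from 9 to 16 (0.1975 at 9 and at 16, 0.2033 at 11). Taking the longer arm from the point estimate instead of half the length does not help; its maximum is 0.215.

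**Which n gives 0.19?** Maximum Clopper-Pearson half-width:

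| n | 24 | 25 | 26 | 27 | 28 | 29 | 30 | 36 | 40 |
|---|---|---|---|---|---|---|---|---|---|
| maximum | 0.2088 | 0.2045 | 0.2007 | 0.1969 | 0.1935 | 0.1901 | 0.1870 | 0.1708 | 0.1620 |

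Rounding to 0.19 needs 28 to 30 subjects; staying at or below 0.19 needs 30. Since the text says up to 25, smaller n only makes it worse.

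**Which method gives 0.19 at n = 25?** Maximum half-widths:

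| Method | n = 25 | n = 30 |
|---|---|---|
| Clopper-Pearson | 0.2045 | 0.1870 |
| Blaker | 0.1968 | 0.1803 |
| Wald (not exact) | 0.1960 | 0.1789 |
| Sterne | 0.1935 | 0.1775 |
| mid-P (not strictly exact) | 0.1903 | 0.1747 |
| Jeffreys (not exact) | 0.1868 | 0.1720 |
| Wilson (not exact) | 0.1824 | 0.1685 |

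**Possible origin.** Section 16.2 of the superseded original protocol reads "A sample size of up to 30, will allow us to estimate an overall safety rate with a maximum 95% exact confidence interval half-width", with the same 0.19. At n = 30 Clopper-Pearson gives 0.187, which rounds to 0.19, while Sterne and mid-P do not. This suggests that 0.19 was computed for 30 and kept when the sentence became "A sample size of up to 25, will allow us to estimate an overall safety rate". That is an inference. The synopsis of the same original protocol already paired 0.19 with about 25. The superseded text is cited for origin only; the error does not depend on it.

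**The case against.** The strongest objection is that the documents say exact without naming Clopper-Pearson. Sterne's interval is also exact and gives 0.1935 at n = 25, so the stated number can be obtained at the stated n by a recognised method. This is true, and it limits the finding to the usual reading of the word. It does not rescue the text: neither document mentions Sterne or mid-P, an unqualified exact binomial interval is ordinarily Clopper-Pearson, and a reader cannot reproduce 0.19 from what is written.

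A second objection is that the figure is marked approximate and the synopsis says about 25. Rounding covers a small discrepancy, but 0.2045 rounds to 0.20, and a figure described as a maximum should not be exceeded by 0.0145.

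A third is that almost nothing follows from it, and this largely stands. No rule, boundary or sample size uses the figure. SAP Section 9 plans counts and percentages and no confidence interval for a safety rate. Near the 30% toxicity rate that the protocol calls acceptable, the half-width is close to 0.19 (0.187 at 7/25, 0.193 at 8/25). For the set actually analysed, 0.19 is conservative: 0.171 at 36 and 0.162 at 40.

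The origin account is also fairly called conjecture, and nothing here rests on it.

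**Conclusion.** The concern holds. For 25 subjects the maximum 95% exact half-width is about 0.20 (0.2045), and the stated 0.19 is 7.1% too narrow. This assumes a two-sided Clopper-Pearson interval, half-width taken as half the interval length, and the maximum over all possible counts. The arithmetic under those assumptions is certain; the only open point is the unnamed method. The importance is low. It is a descriptive precision statement, slightly too favourable for the n it names, while the safety analysis will have a larger denominator and better precision than stated.

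**What to change.** In the protocol synopsis, Protocol Section 16.2 and SAP Section 4.1, replace 0.19 with 0.20, name Clopper-Pearson as the exact method, and tie the figure to 25 subjects. If the sponsor's records show that a different exact interval was used, the alternative is to keep 0.19 and name that interval.

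Optionally add that the maximum is about 0.17 for the planned maximum of 36, since safety covers all dosed subjects. In the SAP only, about 0.16 for the 40 treated could be added, labelled as the realised count.

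The cost is wording in three places. The figure for 25 becomes slightly less favourable; no rule, boundary or sample size changes.
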